8.1 Inclusion Criteria

Individuals must meet all of the following criteria to be included in the study:

1. Adults willing and able to provide informed consent before performing study procedures
2. Adults aged ≥ 18 years at time of informed consent
3. Subjects must have written notification of laboratory confirmed COVID-19 infection performed prior to screening, at a local laboratory by RT-PCR or other commercial or public health assay in any specimen. Subjects should be randomized within 72 hours of receiving this notification.

(NOTE: all subjects will also undergo RT-PCR testing of mid-turbinate samples at a central laboratory on a specimen collected during the Screening/Baseline and Day 1 visit, but entry to the study is based on previously completed local testing for clinical purposes).

4. Have a mild or moderate form of COVID-19 defined as a SpO₂ > 94% at screening
5. Subjects must have at least 1 of the following risk factors for severe illness:
 - a. Aged 65 years or older
 - b. Hypertension
 - c. Diabetes mellitus
 - d. Chronic lung disease including asthma, chronic obstructive pulmonary disease (COPD), and interstitial lung disease (e.g., idiopathic pulmonary fibrosis)
 - e. Chronic cardiac conditions, including coronary artery disease (CAD), heart failure, congenital heart disease, cardiomyopathy
 - f. Severe obesity (body mass index [BMI] ≥ 40 kg/m²)
 - g. Chronic liver disease, including cirrhosis
6. Must agree not to enroll in another study of an investigational agent or take any other drug that has been granted Emergency Use Authorization prior to completion of Day 28
7. If women of childbearing potential (WOCBP) or men whose sexual partners are WOCBP, must be able and willing to use at least 1 highly effective method of contraception during the study and for 90 days after receiving the last dose of study drug. A female subject is considered to be a WOCBP following menarche and until she is in a postmenopausal state for 12 months or otherwise permanently sterile (for which acceptable methods include hysterectomy, bilateral salpingectomy, and bilateral oophorectomy). Contraceptive use by men or women should be consistent with local regulations regarding the methods of

contraception for those participating in clinical studies. Information on contraceptive use during the study is presented in [Appendix 1](#).

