8.2 Exclusion Criteria

Individuals meeting any of the following criteria at screening or baseline are ineligible to participate in this study:

1. Physician makes a decision that trial involvement is not in subjects' best interest, or any condition that does not allow the protocol to be followed safely
2. Known severe liver disease (e.g., Child Pugh score > 12, AST > 5 times upper limit)
3. Oxygen saturation (SaO₂)/SpO₂ ≤ 94% in room air condition, or the arterial oxygen partial pressure (PaO₂)/fractional inspired oxygen (FiO₂) ratio < 300 mmHg
4. Known allergic reaction to camostat mesilate or one of its excipients
5. Known severe renal impairment or receiving dialysis
6. Pregnant or breastfeeding, or positive pregnancy test in a pre-dose examination
7. Receipt of any experimental treatment for COVID-19, including agents with actual or possible direct acting antiviral activity, including, but not limited to, hydroxychloroquine, lopinavir/ritonavir, tocilizumab, ivermectin, or remdesivir within the 30 days prior to the time of the screening evaluation. No off-label use of a drug for COVID-19 is allowed.
8. History of human immunodeficiency virus infection on highly active antiretroviral therapy (HAART).

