10.1 Study Visits

10.1.1 Screening/Baseline and Day 1 Visit

The following procedures and assessments will be done at the onsite Screening/Baseline and Day 1 visit:

- Verify subject has written notification from a local laboratory confirming COVID-19 infection within 72 hours of randomization (i.e., Day 1). In most instances, the Screening/Baseline visit will occur on the same date as Day 1. If needed, the Screening/Baseline may occur before Day 1 as long as randomization can be completed within the 72-hour window.
- Obtain informed consent
- Review of inclusion/exclusion criteria, including urine pregnancy test, if applicable
- Assign a subject ID number (ID number = XXX site number followed by 001, 002, 003 subject number)
- Obtain mid-turbinate nasal swab sample to be sent to the central laboratory to test for a baseline assessment and to test for viral shedding of COVID-19 by RT-PCR
- Draw blood for central laboratory testing
- Record demographics, medical history (including current COVID-19 symptoms), and concomitant medications
- Obtain vital signs (height, weight, heart rate, blood pressure, SpO2)
- Measure oral body temperature
- Perform randomization and dispensing of study drug
- Provide subject with instructions for accessing eDiary portal for collection of daily information
- Administer first dose of study drug after all assessments are completed
- Record of any TEAEs

10.1.2 Onsite Visits on Day 7, Day 15, Unscheduled Visit, Early Termination Visits / Telephone Visits on Day 21, Day 28

The following procedures and assessments will be done on Day 7, Day 15, Day 21, Day 28, and early termination by telephone or at onsite visits:

- Verify subject compliance for completing daily eDiary entries by accessing the web portal for the subject's eDiary
- Review concomitant medications and record any TEAEs
- Assess vital signs (heart rate, blood pressure, SpO2) during on-site visits only
- Measure oral body temperature
- Draw blood for central laboratory testing (Day 15, Unscheduled Visit and Early Termination) during on-site visits only

- Obtain mid-turbinate nasal swab sample for viral shedding test (Day 7, Day 15, and Early Termination Visits) for central laboratory during on-site visits only

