4.1.4 Sample Size Determination for the Primary Efficacy Hypothesis

Sample size determination assumed event rates of 15% and 30% in the active and placebo groups, respectively, 2:1 randomization, and a two-sided type 1 error rate of $\alpha=0.05$. Under these assumptions, an adjusted chi-square test will have 80% power for sample sizes of 186 and 93 in the investigational and placebo arms, respectively (total sample size = 279). The sample size is increased by approximately 7.5% to allow for up to 200 and 100, respectively, to account for loss-to-follow-up.

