4.1.7 Handling of Missing Data for the Primary Efficacy Test

To provide a true ITT efficacy test, subjects lost-to-follow-up prior to Day 28 must be imputed. A multiple imputation (MI) (Rubin and Schenker 1991)³ strategy will be used in the primary efficacy test followed by a completers analysis and a tipping point analysis as sensitivity analyses that examine the robustness of the Missing at Random (MAR) assumption necessary for valid application of MI.

To implement the MI for primary efficacy testing, 20 imputed data sets will be constructed. If the pattern of missing data is not monotonic, a fully conditional (FCS) approach as implemented in SAS PROC MI (SAS Institute)⁴ will be utilized. If the pattern of missing data is monotonic, a regression approach may be used. The MI model will include age, BMI, sex, and the number of days since first COVID-19 symptom (≤ 5 or > 5 days), as well as temperature at Day 7 and 14 taken at the clinic. Should the pattern of missing data be non-monotonic, an FCS model will be utilized. The estimated treatment group difference and standard error will be determined for each imputed data set and combined using Rubin's rule as implemented in SAS PROC MIANALZE. The final treatment group difference will be the average of the multiple imputed datasets. The standard error, p-value, and width of the confidence interval will account for both within and between imputation error.

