The validity of the MI depends on the assumption of Missing at Random (MAR). MAR means that the likelihood of missingness does not depend on the unobserved event status. A tipping point analysis will be performed to evaluate the robustness of this assumption. First a completer's analysis will be performed in which only subjects with complete endpoint status (that is, did not withdraw early or discontinue) are included. Then, all subjects with missing data are included in the analysis varying the numbers of subjects assumed to have experienced the event in both groups separately. This analysis includes the worst-case scenario in which all missing treated subjects are assumed to have experienced the event and all placebo subjects are assumed to have not experienced the event. It also includes the best-case scenario, in which all missing treated subjects are assumed to have not experienced the event and all placebo subjects are assumed to have experienced the event. All other scenarios are similarly evaluated. Assuming superiority has been demonstrated, the percentage of scenarios in which the results change from rejecting the null hypothesis to not rejecting the null hypothesis is determined.

If this percentage of scenarios in which study conclusions change is small (for example, less than 20%), then the superiority conclusion has been shown to be robust with regard to missing data.

As requested by FDA, an additional sensitivity will be provided in which all missing data are treated as failures.

If an exact test is necessary for the primary endpoint due to expected cell counts < 5 in either group, only the tipping point analysis based on the exact tests will be provided.

³ Rubin DB and Schenker N. Multiple imputation in health-care databases: an overview and some applications. *Statistics in Medicine* 10: 585-598, 1991.

⁴ Version 9.4, SAS Institute Inc, Cary, NC

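### The imputation list for the primary test (SAP 4.1.7) omits treatment arm and SpO2, and the completers definition drops withdrawn subjects with known outcomes: small effects, cheap to mend

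*SAP*

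**What the plan says.** SAP 4.1.7 uses multiple imputation (MI) with 20 data sets, under missing at random (MAR), for the primary ITT test. It applies to subjects lost to follow-up before Day 28. The variables are given as "The MI model will include age, BMI, sex, and the number of days since first COVID-19 symptom" (split at 5 days), "as well as temperature at Day 7 and 14 taken at the clinic". Neither treatment arm nor SpO2 appears. SAP 4.1.6 sets out a multivariable model with the same four baseline covariates and does state that treatment group is included.

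SpO2 is how the Protocol defines severity. Inclusion criterion 4 (Protocol 8.1) reads "Have a mild or moderate form of COVID-19 defined as a" saturation above 94%, and exclusion criterion 3 (Protocol 8.2) rules out values at or below "94% in room air condition". It is recorded at baseline, and for later visits Protocol 10.1.2 says "Assess vital signs (heart rate, blood pressure, SpO2) during on-site visits only". Those are Day 7, Day 15, unscheduled and Early Termination visits.

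For the completers sensitivity analysis, SAP 4.1.7 says "only subjects with complete endpoint status (that is, did not withdraw early or discontinue) are included". Protocol 8.5, by contrast, asks sites to keep following discontinued subjects to Day 28 for all outcomes, except after death, hospitalization, withdrawn consent or loss to follow-up. Protocol 6.2.2 also has discontinued subjects followed to Day 28.

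If an exact test is needed because expected counts are below five, "only the tipping point analysis based on the exact tests will be provided".

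**The concern.** There are three separate issues.

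- **Arm.** If the outcome is imputed from a model without treatment, lost subjects in both arms receive a common risk and the arms are pulled together. This needs no informative loss at all.
- **SpO2.** MAR is plausible only given what is in the model. If some subjects disappear while getting worse, age, BMI, sex, symptom duration and temperature may not carry that information, and the imputed risk would be too low. Temperature is an imperfect marker because acetaminophen is allowed for fever (Protocol 9.6.1).
- **Completers.** This analysis is meant to test the MAR assumption. If withdrawn subjects with a recorded hospitalization, or known to be event-free at Day 28, are left out, it introduces a selection of its own.

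The first two bear on the primary estimate and p-value. The third bears only on a sensitivity row.

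**Working it through.** **1. The plan's loss allowance.** SAP 4.1.4 states: "The sample size is increased by approximately 7.5% to allow for up to 200 and 100, respectively, to account for loss-to-follow-up". Check: 186 + 93 = 279, and 279 × 1.075 = 299.9. The allowance is 300 − 279 = 21 subjects, 7 placebo and 14 camostat, or 7% per arm. Expected events are 93 × 0.30 = 27.9 and 186 × 0.15 = 27.9, matching the figure of nearly 28 per arm in SAP 4.1.3.

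**2. Imputing without arm, all loss random.** The common observed risk is (27.9 + 27.9) / 279 = 20%.
- Placebo: (27.9 + 7 × 0.20) / 100 = 29.3%.
- Camostat: (27.9 + 14 × 0.20) / 200 = 15.35%.
- Difference: 13.95 points against a true 15.0.

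A simulation (3,000 trials, 100 placebo and 200 camostat, 20 imputations, Rubin's rules) gives a bias of 0.97 points toward the null without arm and 0.05 with it, and power of 76.7% against 79.8%. A second, simpler simulation gives power of 77.3% against 80.6%.

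**3. Leaving out SpO2, arm included.** The documents give no rate of loss due to deterioration and no correlation between SpO2 and risk, so everything here is assumed. Total loss is fixed at 21. Either 4 + 4 or 8 + 8 subjects (placebo + camostat) are lost while deteriorating, with event proportions of about 0.65 and 0.46, and the rest at random. Day 7 SpO2 correlates with latent severity at about 0.8 (strong) or 0.5 (weak), and Day 7 temperature at about 0.45. Entries are bias toward the null in points, without SpO2 → with it, and the amount recovered.

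| Day 7 SpO2 | 4 + 4 | 8 + 8 |
|---|---|---|
| Strong, seen in all lost | 0.57 → 0.21 (0.36) | 1.24 → 0.57 (0.67) |
| Strong, seen in half | 0.68 → 0.48 (0.20) | 1.43 → 1.01 (0.42) |
| Weak, seen in all lost | 0.61 → 0.45 (0.16) | 1.17 → 0.91 (0.26) |
| Weak, seen in half | 0.68 → 0.59 (0.09) | 1.35 → 1.17 (0.18) |
| Lost before Day 7 | about 0.7 either way (0.05–0.10) | about 1.4 either way (0.05–0.10) |

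The last row comes from a separate run of 1,200 trials per case. Power in the first four rows is 76.5–77.7% without and 77.2–78.5% with SpO2 at 4 + 4, and 73.6–74.7% against 74.7–77.8% at 8 + 8.

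With no true effect (20% in both arms), rejection in favor of camostat (nominal 2.5%) was:
- deterioration loss 0 + 12: 4.6–5.3% without SpO2, 3.2–4.8% with it;
- 3 + 12: 2.8–3.3% and 2.6–3.0%;
- 6 + 12 (6% of each arm): 2.0–2.2% either way.

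**4. Completers.** If a fraction d of each arm withdraws with a known event rate r and is dropped, the remaining rate is (p − d·r) / (1 − d). With d = 7%:
- r = 60% in both arms: 25.8 / 0.93 = 27.74% and 10.8 / 0.93 = 11.61%, difference 16.1 points.
- r = 60% placebo, 30% camostat: 27.74% and 12.9 / 0.93 = 13.87%, difference 13.9 points.
- r equal to each arm's own average: difference 15.0, no shift.

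Dropping 8 + 8 subjects at 0.65 and 0.46 gives (30 − 5.2) / 92 = 26.96% and (30 − 3.68) / 192 = 13.71%, difference 13.25 points. In simulation, keeping the known outcomes brings the 8 + 8 bias to about zero (−0.02 to +0.02).

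**The case against.** The best case for the plan has five parts.

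- **Mechanism.** Becoming ineligible under the entry criteria is a listed withdrawal reason, but Protocol 8.5 follows such subjects to Day 28, and a deteriorating subject who reaches an emergency room or hospital is a recorded event (SAP 3.1). Only silent loss or withdrawn consent among deteriorating subjects remains. This stands, and it limits how much informative loss is plausible.
- **Data.** Subjects who stop attending have no later SpO2, and baseline SpO2 is truncated above 94% by eligibility. This stands, which is why the gain can be close to zero.
- **Assumptions.** SpO2 was always given a stronger link to severity than temperature, only Day 7 temperature was modeled although the SAP lists two time points, and 8 placebo losses exceed the plan's allowance of 7 in that arm. All true. The upper figures are favorable cases.
- **Convention.** A programmer may include arm as a matter of course. Possibly, but 4.1.6 names it and 4.1.7 does not, and the variable list is the only instruction on the point.
- **Completers wording.** The bracket may be a loose gloss for lacking Day 28 status, since the next step in 4.1.7 speaks of subjects with missing data. That is a fair reading, but as written a withdrawn subject with a known outcome belongs to neither group.

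The planned tipping-point, best-case, worst-case and missing-as-failure analyses would show sensitivity to informative loss. They would not correct the primary estimate.

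**Conclusion.** The concern holds as a minor point. The omission of arm has the firmest arithmetic: about 1 point toward the null and about 3 points of power at the planned 7% loss, conditional on the list being programmed as written. The SpO2 gain runs from about 0 to about 0.4 points (4 + 4) or 0.7 points (8 + 8, strong marker seen in every lost subject), and rests wholly on assumed loss and correlation. Both apply only on the chi-square route. The completers wording shifts one sensitivity analysis by roughly 1 to 2 points, with a sign that depends on the withdrawn subjects' risk.

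A reader might infer more, and the documents do not support it:
- *That omitting SpO2 makes a false positive likely.* Clear inflation appeared only when deterioration loss fell entirely on camostat. It was slight at 3 + 12 and absent at 6% in each arm. Nothing in the documents suggests such an imbalance, and adding SpO2 removes only part of it.
- *That withdrawal for worsening leaves the primary outcome missing.* Protocol 8.5 keeps such subjects under follow-up.
- *That the completers rule biases the primary test.* That test imputes only subjects lost to follow-up, so withdrawn subjects with known outcomes stay in it.

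**What to change.** Two changes to SAP 4.1.7 before unblinding:

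1. Name treatment arm in the imputation model, and add baseline SpO2 and the last on-site SpO2 (Day 7, or Early Termination if earlier), both as continuous variables.
2. Replace the completers bracket with: known hospitalization/ER visit or death, or known event-free status through Day 28, regardless of withdrawal or drug discontinuation.

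No new data are needed. SpO2 must itself be imputed where it is missing, for which 4.1.7 already provides a fully conditional route. Imputation variance rises slightly: the standard error of the difference goes from 5.30 to 5.34 points in the 8 + 8 case with SpO2 seen in half of lost subjects. Only part of any bias from informative loss is recovered, so the planned sensitivity analyses should stay.

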8.5 Study Withdrawal, Removal, and Discontinuation of Subjects

Subjects who discontinue study treatment or who are withdrawn from the study for any reason must have the date and the reason for study discontinuation recorded on the electronic case

report form (eCRF). Subjects who discontinue early from the study will be asked to return to the study site within 3 to 7 days of the last administration of study drug to complete assessments as indicated in the Schedule of Assessments ([Table 1](#)) (Early Termination Visit).

In the event that a subject discontinues prematurely from the study because of a TEAE or SAE, the TEAE or SAE will be followed up until it resolves (returns to normal or baseline values) or stabilizes, or until it is judged by the investigator to no longer be clinically significant and thereafter until Day 28.

Upon discontinuation every effort will be made to follow the subjects until Day 28 for all study outcomes unless there is death of the subject, hospitalization, withdrawal of consent by the subject or the subject is lost to follow up.

Once a subject is withdrawn from the study, the subject may not reenter the study.

A subject may voluntarily withdraw or be withdrawn from the study at any time for reasons including, but not limited to, the following:

- AE and/or SAE
- subject withdrawal of consent: at any time, a subject's participation in the study may be terminated at his/her request or on the basis of the investigator's clinical judgment. The reason for subject withdrawal will be noted on the eCRF.
- intercurrent illness: a condition, injury, or disease unrelated to the primary diagnosis that became apparent during treatment and necessitated the subject's termination from the study
- general or specific changes in the subject's condition that renders him/her ineligible for further treatment according to the inclusion/exclusion criteria
- subject fails to adhere to the protocol requirements (e.g., drug noncompliance, failure to return for defined number of visits)
- lost to follow-up: the subject stopped coming for visits, and study personnel were unable to contact the subject
- pregnancy, as indicated in [Section 12.4.5](#).

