2.3.3 Safety/Tolerability

- Incidence of AEs and SAEs of any grade from randomization up to Day 28.

- Cumulative incidence of grade 3 and 4 AEs from randomization up to Day 28.
- Incidence of discontinuation from study due to an AE/SAE (discontinued subjects will be followed up until Day 28).
- Change from baseline in clinical laboratory parameters (including platelet counts, liver function tests, and potassium levels, etc.).
- Change from baseline in vital signs (heart rate, blood pressure, peripheral capillary oxygen saturation [SpO₂]).

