3.1 PRIMARY ANALYSIS

Disease Progression (Hospitalization): The Primary Efficacy Endpoint is defined as status changing from ambulatory care to COVID-19 related hospitalization, ER visit, or death due to any cause on or prior to Day 28. Presenting to the emergency room is considered hospitalization. Hospitalization/ER visit and Death are recorded on the End of Study (EOS) form and will support the primary endpoint analysis. All subjects who have an End of Study form with any Hospitalization/ER Visit or Death are assumed to be COVID-related and therefore analyzed as a failure of the primary endpoint. Subjects failing the primary endpoint will be described within the Clinical Study Report.

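### The completers analysis is defined by disposition rather than by endpoint status, so as written it drops subjects whose Day 28 outcome is known

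*SAP*

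**What the plan says.** SAP 4.1.7 bases the primary test on multiple imputation, on the ground that "subjects lost-to-follow-up prior to Day 28 must be imputed". This is "followed by a completers analysis and a tipping point analysis as sensitivity analyses that examine the robustness of the Missing at Random (MAR) assumption". The completers rule is "only subjects with complete endpoint status (that is, did not withdraw early or discontinue) are included". The tipping-point step then adds the subjects with missing data and varies their assumed outcomes. A further analysis, requested by the FDA, counts all missing outcomes as failures. Draft Table 14.2.1.1 gives the completers result its own row, with a p-value and confidence interval.

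Three other places bear on whose outcome is known:

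- SAP 3.1 defines the endpoint as "status changing from ambulatory care to COVID-19 related hospitalization, ER visit, or death due to any cause on or prior to Day 28". On the source of the data it says "All subjects who have an End of Study form with any Hospitalization/ER Visit or Death are assumed to be COVID-related", and such subjects are analyzed as failures. No condition on disposition is attached.
- Protocol 8.5 asks for every effort to follow subjects to Day 28 after discontinuation, "unless there is death of the subject, hospitalization, withdrawal of consent by the subject or the subject is lost to follow up".
- SAP 2.3.3, on discontinuation from the study because of an adverse event, notes that "discontinued subjects will be followed up until Day 28".

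**The concern.** For a first-event endpoint, having a complete outcome and having completed the study are different things. One hospitalization, ER visit or death by Day 28 fixes the outcome as failure, whatever happens to the subject afterwards. A subject who stops early but is followed to Day 28 without an event also has a final outcome. The parenthesis in SAP 4.1.7 treats both as incomplete.

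A completers analysis is meant to show what the observed outcomes say without imputation. If it also discards observed outcomes, a gap between it and the primary result no longer isolates the effect of missing data. Agreement between the two is weaker reassurance for the same reason.

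The boundary also matters for the tipping-point grid. A known-event subject who is excluded as a non-completer is either left out of the grid or, if counted as missing, given hypothetical outcomes that include event-free.

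**Working it through.** **Step 1. Apply the texts to three kinds of subject.**

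| Subject | Outcome under SAP 3.1 | Completers rule in SAP 4.1.7 |
|---|---|---|
| ER visit on Day 5, then withdraws | Failure, final | Excluded |
| Stops early, followed event-free to Day 28 | Event-free, final | Excluded if the stop counts as discontinuing |
| Lost on Day 10, no event recorded | Unknown | Excluded |

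Only the third subject has a missing outcome. The SAP rule does not say whether discontinuing refers to drug or study. Protocol 8.5 covers both in one sentence, and SAP 4.3.1 lists them as separate items. No section says that a subject with an observed event stays in the completers set regardless of disposition.

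**Step 2. Reproduce the design figures.** The plan gives no figure for this rule, so the anchor is the sample-size statement in SAP 4.1.4: 15% versus 30%, 2:1, two-sided 0.05, 186 + 93 = 279, 80% power. Exact binomial enumeration at 186/93 gives 80.2% (Fisher) and 78.9% (continuity-corrected chi-square), close to the stated 80%. Inflation: 279 × 1.075 = 299.9, hence 200/100. Expected events at 200/100 are 200 × 0.15 = 30 and 100 × 0.30 = 30.

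**Step 3. Illustrate the effect of the rule.** The documents do not say how many subjects would have an event and then withdraw or discontinue. The dropped shares below are therefore assumptions. With a share f of event subjects dropped in an arm of size N with E events, and all event-free subjects retained:

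rate = E(1 − f) / (N − E·f)

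| f active / f placebo | Active | Placebo | Difference (points) | p, uncorrected chi-square |
|---|---|---|---|---|
| 0 / 0 | 30/200 = 15.0% | 30/100 = 30.0% | -15.0 | 0.0022 |
| 10% / 10% | 27/197 = 13.7% | 27/97 = 27.8% | -14.1 | 0.003 |
| 25% / 25% | 22.5/192.5 = 11.7% | 22.5/92.5 = 24.3% | -12.6 | 0.006 |
| 50% / 50% | 15/185 = 8.1% | 15/85 = 17.6% | -9.5 | 0.021 |
| 50% / 25% | 15/185 = 8.1% | 22.5/92.5 = 24.3% | -16.2 | 0.0002 |
| 25% / 50% | 22.5/192.5 = 11.7% | 15/85 = 17.6% | -6.0 | 0.18 |

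The p-values are computed at expected counts, some of them fractional, and only show scale.

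**Step 4. Let the rule remove event-free subjects too.** Expected event-free subjects are 170 and 70.

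- Dropping 25% of events and 7.5% of event-free subjects in both arms: 22.5/(22.5 + 157.25) = 12.5% and 22.5/(22.5 + 64.75) = 25.8%, a difference of -13.3 points rather than -12.6.
- Dropping 25% of each: 22.5/150 = 15% and 22.5/75 = 30%, so no change.

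**The case against.** The best defence is that complete endpoint status is the operative criterion and the parenthesis only a loose gloss. Read with SAP 3.1, a subject with a recorded event has complete status, and a careful programmer would keep that subject. This shows that the sentence is at odds with itself, but it does not remove the problem. The words that introduce the parenthesis make disposition the working definition, and nothing elsewhere overrides it.

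Four stronger readings are tempting, and the documents do not support them:

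- *Hospitalization leads to exclusion.* A reader might infer from Protocol 8.5 that having the event ends participation. That sentence concerns subjects who have already discontinued and lists when further follow-up may stop. Hospitalization is not among the withdrawal reasons named there, although that list is not exhaustive. Overlap between events and discontinuation is foreseeable, but it is not prescribed.
- *This is the main check on the imputation.* It is one of several. The only robustness criterion, the example of under 20% of scenarios changing the conclusion, belongs to the tipping-point grid. If the exact test is triggered, SAP 4.1.7 provides only the tipping-point analysis.
- *The effect always shrinks, with a large loss of power.* Shrinkage follows from equal, event-only losses. Unequal losses can widen the difference, and event-free losses can offset the shrinkage. At a 10% share the change is under one point. A 50% share means 30 of the 60 expected events, more than the 21 subjects (300 − 279) allowed for loss to follow-up; that allowance is for a different group but gives a sense of scale. Power is also a poor yardstick for a sensitivity analysis that was not powered.
- *The primary test discards known events.* The completers rule does not define the imputation. SAP 4.1.7 does not say that an event seen before loss to follow-up is kept rather than imputed, but that is silence, not a rule to overwrite it.

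**Conclusion.** The point holds as a defect in a stated rule. SAP 4.1.7 equates endpoint completeness with not having withdrawn or discontinued, and under SAP 3.1 the two differ. As written, the completers row of Table 14.2.1.1 leaves out subjects with a known event and subjects known to be event-free who stopped early. The consequence is possible bias in one planned sensitivity analysis, with knock-on ambiguity about who enters the tipping-point grid.

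The size and direction cannot be determined from the documents. Under the design rates the illustrations run from -16.2 to -6.0 points against -15.0. They rest on assumed dropped shares and on keeping every event-free subject. If few subjects have an event and then stop, the effect is small.

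**What to change.** Replace the parenthesis in SAP 4.1.7 with a definition based on the outcome. A completer is a subject with an observed primary endpoint event on or before Day 28, or one known to be event-free at Day 28, whatever the drug or study disposition. Every other randomized subject has a missing primary outcome. State that this one definition decides whose outcome is imputed, who enters the tipping-point grid (including its exact-test version) and who is counted as a failure in the all-missing-as-failure analysis.

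The cost is a sentence or two in the SAP, made before unblinding. It needs no new data collection and no change to study procedures.
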